## 3.1.1 Administrative structure of the trial

Boehringer Ingelheim is the Sponsor of this trial. The Coordinating Investigator and participating investigators will be physicians experienced and specialized in the treatment of CLL and in the conduct of phase I trials.

A Data Safety Monitoring Board (DSMB) will perform regular safety assessments, provide recommendations for dose escalation and whether to continue, modify or to terminate the trial. Frequency of meetings, functions and responsibilities of the DSMB will be described in the DSMB Charter.

# **3.2 DISCUSSION OF TRIAL DESIGN, INCLUDING THE CHOICE OF CONTROL GROUP**

The primary objective of this trial is to determine the MTD. The most important secondary objective is to assess the safety of BI 836826. This can be achieved by an open label, single arm trial design without a control group.

Adult patients with CLL who experience a relapse after at least two prior treatment regimens are considered eligible for this trial. Treatment options in this population are limited, in particular in patients with adverse prognostic markers, such as deletion 17p, who frequently do not reach durable responses or a long progression free interval after standard chemotherapy based regimens.

The investigational drug BI 836826 will be administered as monotherapy. At the lowest dose cohorts, single patients are to be enrolled to limit the number of patients who are receiving doses of the drug which may not exert a relevant pharmacodynamic effect in humans. Stipulated by drug related adverse events CTCAE grade 2 or higher or the documentation of a threshold pharmacodynamic activity as defined in Section 3.1, cohorts of single patients will be expanded to cohorts of at least 3 patients, and the trial design will follow a standard 3+3 design with dose escalation and de-escalation. Once the MTD has been defined, an expansion cohort of 12-30 patients is planned to be enrolled to better characterize the safety profile and tolerability of the MTD.

At screening, blood samples and a physical examination including a clinical assessment of CLL are done and the patient is evaluated for eligibility in the trial. Evaluation of bone

**Trial Protocol** 

will be performed at all visits

marrow and CT scan may be performed at the discretion of the investigator. Results should be reported in case these examinations have been performed within 4 weeks prior to screening.

A patient enrolled in a cohort during dose escalation may receive up to 4 courses of BI 836826. In patients who unequivocally show clinical benefit from the drug, the administration of 4 additional treatment courses may be possible in agreement between the investigator and the Clinical Monitor at Boehringer Ingelheim. Provided that the administration of 4 courses is considered safe, up to 8 courses may be administered for patients enrolled in the expansion cohort.

Each patient will be closely monitored for infusion-related reactions and tumour lysis syndrome.

Safety

during the treatment phase.

Disease status will be assessed every two weeks until the EOT visit, including physical examination, clinical assessment of CLL and blood samples. At the discretion of the investigator (i.e., if medically indicated), a CT scan and a bone marrow examination may be performed to confirm a CR 8 weeks after a patient for the first time meets the criteria of a CR. Results of any CT scan or bone marrow examination performed during the conduct of the trial should be reported in the eCRF.

During the follow-up phase, disease status evaluations (physical examination, clinical assessment of CLL, and blood samples) should be performed at least every 4 weeks for 6 months after the EOT visit. More frequent visits may be indicated, e.g. for follow-up of laboratory parameters or adverse events which have not been resolved at the EOT visit.

## 3.3 SELECTION OF TRIAL POPULATION

## 3.3.1 Main diagnosis for study entry

Patients with chronic lymphocytic leukaemia will be eligible for this trial.

## 3.3.2 Inclusion criteria

- 1. Diagnosis of relapsed or refractory chronic lymphocytic leukaemia (according to the definition of the IWCLL (R10-4429))
- 2. Previous therapy of CLL with at least two prior treatment regimens
- 3. At least one of the following criteria for active disease as defined by the IWCLL
  - (1) Evidence of progressive marrow failure as manifested by the development or worsening of anemia and/or thrombocytopenia
  - (2) Massive (i.e. at least 6 cm below the left costal margin) or progressive or symptomatic splenomegaly as assessed by the investigator;
  - (3) Massive nodes (i.e. at least 10 cm in longest diameter) or progressive or symptomatic lymphadenopathy as assessed by the investigator

- (4) Progressive lymphocytosis with an increase of more than 50% over a 2-month period or a lymphocyte doubling time of less than 6 months
- (5) Constitutional symptoms, defined as any one or more of the following disease-related symptoms or signs:
  - Unintentional weight loss of 10% or more within the previous 6 months
  - Fevers higher than 38.0°C for 2 or more weeks without other evidence of infection
  - Night sweats for more than 1 month without evidence of infection
- 4. Absolute lymphocyte count lower than  $200 \times 10^9$ /l
- 5. ECOG Performance Status 0, 1 or 2
- 6. Age  $\geq$  18 years.
- 7. Written informed consent which is consistent with ICH-GCP guidelines and local legislation

## 3.3.3 Exclusion criteria

- 1. Prior treatment with anti CD 20 therapy within 4 weeks, or alemtuzumab within 8 weeks, or any **cytotoxic** antileukemia therapy within 2 weeks, **Ibrutinib or Idelalisib within 1** week prior to the first administration of the trial drug
- 2. Prior allogeneic stem cell transplantation
- 3. Active autoimmune haemolytic anemia
- 4. Active autoimmune thrombocytopenia
- 5. Known transformation to an aggressive B-cell malignancy (e.g. large B-cell lymphoma, Richter's syndrome)
- 6. Concurrent treatment with systemic glucocorticosteroids at doses equivalent to prednisolone 20 mg/d or higher.
- 7. Prior history of malignancy other than CLL (except basal cell or squamous cell carcinoma of the skin, or carcinoma in situ of the uterine cervix or breast treated with curative therapy) unless the subject has been free of disease and without treatment for at least 5 years.
- 8. AST, and/or ALT > 2.5 x upper limit of normal (CTCAE grade 2 or higher)
- 9. Total bilirubin > 1.5 x upper limit of normal (CTCAE grade 2 or higher)
- 10. ANC  $< 1.0 \times 10^9$ /L (without growth factor support).
- 11. Platelets  $< 25 \times 10^9$ /L (without growth factor support or transfusions)
- 12. Estimated GFR <45 mL/min (see Section 10.3)
- 13. Proteinuria CTCAE grade 2 or higher
- 14. Significant concurrent medical disease or condition which according to the investigator's judgement would either compromise patient safety or interfere with the evaluation of the safety of the test drug.
- 15. Any infectious disease requiring treatment at the time of enrolment or within the previous 2 weeks.
- 16. Active Hepatitis B or Hepatitis C, or laboratory evidence for a chronic infection.
- 17. HIV infection
- 18. CMV viremia
- 19. Women of childbearing potential not using a highly effective method of birth control during the trial until one year after the last dose. Highly effective methods of birth control are defined as those which result in a low failure rate (i.e. less than 1% per year) when

used consistently and correctly such as implants, injectables, combined oral contraceptives, some intrauterine devices (IUDs), sexual abstinence or vasectomised partner. Barrier methods of contraception are accepted if condom or occlusive cap are used together with spermicides (e.g. foam, gel). Female patients will be considered to be of childbearing potential unless surgically sterilised by hysterectomy or bilateral tubal ligation/salpingectomy, or post-menopausal for at least two years.

- 20. Pregnancy or breast feeding.
- 21. Known or suspected active alcohol or drug abuse.
- 22. Treatment with another investigational drug within the past four weeks before start of therapy or concomitantly with this trial.
- 23. Prior treatment with BI 836826.
- 24. Patients unable to comply with the protocol

#### **3.3.4** Removal of patients from therapy or assessments

#### 3.3.4.1 Removal of individual patients

An individual patient is to be withdrawn from the trial if:

- The patient withdraws consent. Patients are free to discontinue their participation in this trial at any time without the need to justify the decision.
- The patient needs concomitant drugs which may interfere with the investigational product (please refer to Section 4.2.2).
- The patient is no longer able to participate for other medical reasons (e.g. adverse events unrelated to therapy or disease progression, concomitant diagnoses, pregnancy, surgery or administrative reasons). The investigator may also stop a patient's participation if the patient is no longer able to attend trial visits.

A patient can be withdrawn after discussion between the investigator and the Clinical Monitor at Boehringer Ingelheim if eligibility criteria are violated and/or the patient fails to comply with the protocol.

All withdrawals will be documented and the reason for withdrawal recorded and discussed, as necessary, in the final report of the trial. As soon as a patient is withdrawn from the trial, the next scheduled visit and the EOT have to be performed if feasible. Every effort should be made to follow-up patients in case an AE is still ongoing at the time of withdrawal.

A patient has to discontinue trial drug administration in case

- A DLT occurs which does not recover to a degree that allows treatment continuation.
- PD or any other concomitant diagnosis/symptom develops resulting in an indication to start any other therapy for CLL, including deterioration of general condition.

Patients who have not completed at least one course will be replaced. Patients who terminate trial treatment due to DLT will not be replaced.

#### 3.3.4.2 Discontinuation of the trial by the sponsor

Boehringer Ingelheim reserves the right to discontinue the trial overall or at a particular trial site at any time for the following reasons:

- 1. Violation of GCP, the CTP, or the contract by a trial site or investigator, disturbing the appropriate conduct of the trial,
- 2. Emergence of any efficacy/safety information that could significantly affect continuation of the trial,
- 3. Failure to meet expected enrolment goals overall or at a particular trial site.

The investigator / the trial site will be reimbursed for reasonable expenses incurred in case of trial termination (except in case of the first reason).

## 3.3.4.2.1 Trial stopping rules in case of unacceptable toxicities

All AEs, including SAEs and deaths will be carefully analyzed by the sponsor. Unacceptable toxicity will be defined as:

- Clinically relevant adverse events that are unexpected considering the mode of action, and are not manifestations of underlying disease or background events typical of the study population
  - o and/or are debilitating, non-reversible, not manageable
  - or lead to a fatal outcome

where evidence suggests that there was a reasonable possibility that the drug caused the adverse event

• Higher than expected frequency of specific events (such as known consequences of the underlying disease or other events that commonly occur in the study population independent of drug therapy) that indicates those events occur more frequently in the drug treatment group than would be expected in the study population.

If one or both of the above criteria are met the enrolment to the trial will be stopped to allow for in-depth analysis of the safety profile of BI836826. The risk-benefit profile of BI 836826 will be re-assessed by the sponsor's trial team, coordinating investigator and DSMB. The outcome of the analysis and the recommendations will be shared with all involved regulatory health authorities prior to a possible re-start of enrolment.

In case the benefit/risk assessment is no longer considered to be positive, the trial will be discontinued.

## 4. **TREATMENTS**

## 4.1 TREATMENTS TO BE ADMINISTERED

In course 1, the total dose will be divided into two portions administered on day 1 and 2 (please refer to the Flow Chart: Course 1, Dosing on Day 1 and Day 2).

The dose on day 1 will be 10% of the total dose, but not exceed 10 mg in case the total dose is higher than 100 mg. The dose on day 2 will be the planned total dose minus the dose administered on day 1. If adverse events which are related to the infusion schedule, e.g. infusion-related reactions or tumour lysis syndrome require administration of a lower dose on day 2, the total dose in course 1 may be divided into 3 smaller portions on day 1, 2 and 8. In this case, the dose on day 1 will remain as defined previously. The difference between day 1 and the planned total dose level will be equally divided between day 2 and 8 (reference to appendix 10.6). The distribution of the planned total dose in course 1 to two, or if needed to three smaller portions will be based on safety data from the previous cohort and will be assessed and may be modified by the DSMB. If supported by the DSMB, the same rules may be applied to course 2 in case infusion-related adverse events can be controlled by the above measures in course 1 but occur in course 2.

In all subsequent treatment courses, BI 836826 will be administered as a rate-controlled intravenous infusion on day 1 of each 14-day course.

The first and second infusion will be started at a rate of 10 mL/h. The infusion rate should be increased every 30 (+/-10) minutes by 10 mL/h to a maximum of 80 mL/h as long as tolerated by the patient. If considered safe by the investigator, the stepwise increase of infusion rate during the third and subsequent infusions may be faster or steps may be omitted, but the maximum infusion rate must not exceed 120 mL/h. If symptoms of an infusion related reaction occur, the infusion should be temporarily stopped. Upon recovery, it should be resumed at 50% of the rate at which the reaction occurred for at least 30 minutes. Lower rates may be selected if clinically indicated. Depending on the time of occurrence and the severity of the reaction, the investigator may consider administering additional supportive medication, e.g. corticosteroids. A stepwise re-increase of the infusion rate to a maximum of 80 mL/h is possible.

For medical reasons, the duration of the infusion may be expanded until the use-by date and use-by time indicated on the label is reached. The actual duration of the infusion needs to be documented in the eCRF including actual start and end time, actual time points for interruption and restart of the infusion and the actual infusion rates.

Adverse events during the infusion should be thoroughly documented and characterized to allow differentiation between infusion-related reactions and tumour lysis syndrome (R10-4428, R10-4517).

#### 4.1.1 Identity of BI investigational product and comparator product(s)

4.1.1.1 BI 836826	
Substance (INN):	BI 836826
Pharmaceutical form:	Solution for infusion after dilution
Source:	Boehringer Ingelheim Pharma GmbH & Co. KG
Unit strength:	10 mg/mL (vials with 10 mL)
Daily dose:	See Section 4.1.3
Duration of use:	One to three single doses within a 14 day course
Route of administration:	Intravenous
Posology:	Rate controlled infusion
	See Section 4.1.6

#### 4.1.2 Method of assigning patients to treatment groups

Not applicable. This is a single arm, open-label, dose escalation trial.

#### 4.1.3 Selection of doses in the trial

BI 836826 will be administered as a rate-controlled, intravenous infusion on day 1, 2 and possibly day 8 in course 1 and on day 1 in the subsequent courses.

A fixed dose of 1 mg BI 836826 per patient was determined to be the safe first in human starting dose for patients with an advanced haematological malignancy. The calculation of the safe starting dose of 1 mg in humans was based on data from studies in Cynomolgus monkeys and from ex vivo experiments with primary B-cells obtained from fresh blood samples of CLL patients. This dose is anticipated to represent a low pharmacologically active dose which may be capable to result in a detectable B-cell reduction in the peripheral blood of CLL patients. For details please refer to the Investigator's Brochure, Section 5.6.3 (U10-1892-01).

The dose is planned to be escalated in cohorts at pre-defined dose levels based on a multiplication factor of approximately 3 in the low dose range, and a factor of 2 at doses higher than 25 mg. The dose levels per treatment course are 1 mg, 3 mg, 9 mg, 25 mg, 50 mg, 100 mg, 200 mg ..., up to 1400 mg. At doses higher than 200 mg, the next dose cohort will be enrolled at a dose which is at maximum two times of the previous dose.

Every time a dose escalation is to be performed, the data of all previous dose cohorts will be reviewed and discussed between the Coordinating Investigator and the sponsor. The same data and the recommendation of the Sponsor and Coordinating investigator will be provided to the DSMB who will be asked to provide an independent assessment including a dose recommendation for the next cohort. As a result, lower dose increments than the predefined levels will be possible.

## 4.1.4 Drug assignment and administration of doses for each patient

Prior to inclusion of a new patient during the dose escalation phase the investigator has to confirm the actual dose tier of BI 836826 for the patient with the Clinical Monitor of the sponsor who oversees the dose escalation steps and the safety data of patients from all trial sites. BI 836826 will be administered as an intravenous infusion under the supervision of the investigator or designated personnel.

BI 836826 may be administered at any time during the day.

All patients have to be monitored for clinical or laboratory evidence of tumour lysis syndrome (see Section 5.2.3.2). To prevent tumour lysis syndrome, all patients should receive appropriate hydration and/or prophylactic drugs according to local standards or published guidelines (R10-4517).

Premedication to prevent infusion-related reactions is obligatory 30 - 120 minutes prior to the first and second administration of BI 836826, unless a contraindication for premedication exists, and should include

- Analgesic/Antipyretic p.o. or i.v., equivalent to Acetaminophen/ or Paracetamol 1000 mg p.o.
- Antihistamine p.o. or i.v., equivalent to Diphenhydramine 50 mg i.v.
- Glucocorticoid i.v., equivalent to prednisolone 100 mg

If BI 836826 has been well tolerated without signs of infusion-related reactions in the first and second course, glucocorticoid premedication may be reduced to 50% of the dose in the previous course starting with the third course. In case the patient has tolerated the 4th treatment course without infusion-related reactions after premedication with doses equivalent to prednisolone 25 mg, the investigator may individually decide whether to administer premedication in courses 5-8.

During the dose-escalation phase, up to 4 courses may be administered. In case of evidence of clinical benefit as judged by the investigator (e.g. PR, CR, disease stabilization, amelioration of CLL related symptoms), treatment with BI 836826 can be continued for another 4 courses after discussion between the Investigator and the Clinical Monitor of the sponsor. During treatment of the expansion cohort, a maximum of 8 courses may be offered to all patients. In the dose-escalation phase as well as in the expansion cohort, in patients who experience sustained benefit and tolerate treatment well, treatment may be continued beyond 8 courses on a case by case basis after discussion between the Investigator and the Clinical Monitor of the sponsor. If patients continue beyond cycle 8, the same assessments will be done as applicable for cycles 5-8. At the end of each treatment course, adverse events and safety laboratory will be assessed. To continue treatment with further courses, **all** of the following criteria must be met:

(1) Neutrophils  $\geq 500 \ /\mu L \ (0.5 \ x \ 10^9/L)$  and platelets  $\geq 25.000 \ /\mu L \ (25 \ x \ 10^9/L)$ , with or without growth-factor support or transfusions.

(2) Acceptable tolerability (in case of an adverse event at the planned start of a treatment course, patients may continue therapy only after recovery to a level which would allow further therapy, i.e. CTCAE grade 1 or pre-treatment value.)

In case criterion 1 and/or 2 is not fulfilled, blood counts and/or the adverse event should be re-evaluated for up to three weeks. Any case of a delay in treatment course should be communicated to the Clinical Monitor at Boehringer Ingelheim. As soon as criterion 1 is met, the investigator in agreement with the Clinical Monitor at Boehringer Ingelheim may continue the treatment (unless other criteria for discontinuation or withdrawal apply, see Section 3.3.4.1). In case an adverse event is continuing at a CTCAE grade 2 or higher without recovery to grade 1 within 5 weeks after the last BI 836826 infusion and this is above the pre-treatment level, the investigator in agreement with the Clinical Monitor at Boehringer Ingelheim may continue BI 836826 only in the case that the event is considered not drug-related by investigator and sponsor.

Administration of the trial drug has to be stopped temporarily in case of a DLT (see Section 5.2.1.1). Patients may continue therapy only after recovery from the DLT to at least CTCAE grade 1 or pre-treatment value. The future dose of BI 836826 must be finally agreed on between the sponsor and the investigator. A reduction of the dose will be allowed only once for an individual patient during the whole trial. Treatment has to be discontinued in case the DLT is not reversible.

Intra-patient dose escalation may be considered in agreement between investigator and sponsor for selected patients. It is restricted to patients who have received at least 4 treatment courses and tolerate the treatment well at the time of dose escalation. Intra-patient dose escalation can only be performed at a time when the next higher dose cohort has been reviewed and considered safe by the DSMB. The dose escalation step is limited the dose which has been administered to the next higher cohort. The treatment courses at the increased dose have to follow the instructions as outlined for course 5-8 in the Flow Chart and the protocol. In addition, after the first dose at the higher dose level, patients have to be monitored for at least 24 hours after the end of the infusion, including safety laboratory for tumour lysis syndrome.

A log of all patients enrolled into the study (i.e. having given informed consent) will be maintained in the ISF at the investigational site irrespective of whether they have been treated with investigational drug or not.

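### The stated premedication duty ends on day 2 of course 1, although the taper in the same section presumes full premedication throughout courses 1 and 2

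*Protocol*

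**What the plan says.** Three parts of Protocol Section 4.1.4 bear on this point.

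- **Duty.** An antipyretic, an antihistamine and a glucocorticoid equivalent to prednisolone 100 mg are obligatory 30-120 minutes "prior to the first and second administration of BI 836826, unless a contraindication for premedication exists".
- **Taper.** If no infusion-related reaction was seen "in the first and second course, glucocorticoid premedication may be reduced to 50% of the dose in the previous course starting with the third course".
- **Discretion.** For a patient who tolerated course 4 without such reactions "after premedication with doses equivalent to prednisolone 25 mg, the investigator may individually decide whether to administer premedication in courses 5-8".

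Protocol Section 4.1 fixes which infusions these are. "In course 1, the total dose will be divided into two portions administered on day 1 and 2". On the size of the first portion it says: "The dose on day 1 will be 10% of the total dose, but not exceed 10 mg" (the cap applies to totals above 100 mg). The rest follows on day 2. If, for example, "infusion-related reactions or tumour lysis syndrome require administration of a lower dose on day 2", the remainder is halved between days 2 and 8. For events that appear only later, and with the DSMB's support, "the same rules may be applied to course 2 in case infusion-related adverse events can be controlled by the above measures in course 1". Otherwise course 2 is a single infusion on its day 1.

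SAP Section 6.2, Table 6.2:1, code C2, flags premedication that was not taken. It then relies on medical review of whether the protocol required it. The code excludes no patient from any analysis set.

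**The concern.** The duty is counted in administrations and the taper in courses. With course 1 split, the two no longer line up: the second administration is day 2 of course 1, while the first permitted reduction comes in course 3. Everything in between is presumed to be premedicated but is not required to be. That is the day 8 portion, the course 2 infusion, and any extra portions of course 2.

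This matters because other precautions relax at the same point. From the third infusion, if the investigator considers it safe, "the stepwise increase of infusion rate during the third and subsequent infusions may be faster or steps may be omitted", up to 120 mL/h instead of 80 mL/h. Protocol Section 5.2.5.1 asks for continuous cardiac monitoring during the first two infusions and leaves later surveillance to the investigator. The third infusion is day 8 in a patient on the three-portion schedule, which exists because of infusion-related problems. Otherwise it is the first undivided full dose. On the analysis side, a C2 reviewer has no stated rule for these infusions, so the same omission could be coded differently from patient to patient.

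**Working it through.** **1. Which infusions are the first and second administration?** Section 4.1 puts them on days 1 and 2 of course 1. Section 5.2.3.2 places the second infusion in course 1, and Section 6.1 speaks of the first two doses in that course. The stated duty therefore ends on day 2.

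**2. Does the taper reproduce its own figure?** Inputs from Section 4.1.4: start at 100 mg, halve the previous course's dose from course 3, 25 mg named at course 4.

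- Full dose in courses 1 and 2, then halving: 100, 100, 100 × 0.5 = 50, 50 × 0.5 = 25 mg. This matches.
- Halving already from course 2: 100, 50, 25, 12.5 mg. No match.
- Halving delayed to course 4: 100, 100, 100, 50 mg. No match.
- No glucocorticoid in course 2: there is nothing to halve.

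Reduction is optional, so other paths can be constructed. Because no text allows a reduction before course 3, the path that fits the wording has 100 mg in course 2.

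**3. What does the discretion sentence add?** It speaks of premedication as a whole, not only the glucocorticoid, and opens the choice only in courses 5-8 after a tolerated course 4. If premedication were already optional from the third infusion, that conditional permission would be empty.

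**4. Does this reach day 8 and split portions of course 2?** Both lie in courses 1 and 2, before the first permitted reduction, so the same course-based inference applies to them. No readable text states a duty there. By contrast, Section 5.2.3.2 extends tumour lysis monitoring by name to day 8 and to one or more infusions in course 2.

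**5. Coverage of the stated duty within courses 1 and 2.**

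- Default: 2 + 1 = 3 administrations, 2 covered.
- Three-portion course 1: 3 + 1 = 4 administrations, 2 covered.
- Course 2 split as well: from 2 + 2 = 4 to 3 + 3 = 6 administrations, 2 covered.

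**6. Size of the infusions outside the duty.** For total dose D: day 1 = min(0.1 × D, 10 mg); default day 2 = D − day 1; three portions, day 2 = day 8 = (D − day 1)/2; unsplit course 2 = D.

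| D (mg) | Day 1 | Day 2, default | Day 8 portion (share of D) | Course 2 ÷ largest earlier infusion, default | Same, three portions |
|---|---|---|---|---|---|
| 100 | 10 | 90 | 45 (45%) | 100/90 = 1.11 | 100/45 = 2.22 |
| 200 | 10 | 190 | 95 (47.5%) | 200/190 = 1.05 | 200/95 = 2.11 |
| 1400 | 10 | 1390 | 695 (49.6%) | 1400/1390 = 1.01 | 1400/695 = 2.01 |

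The shares and ratios at 100 mg hold for every lower total. The permitted maximum rate from the third infusion is 120/80 = 1.5 times that of the first two.

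**The case against.** The strongest reply is that Section 4.1.4, read as a whole, already answers the question: nothing in it permits omission before course 5, so this is one loosely worded sentence and not two conflicting instructions. That is right as far as it goes. A reader might infer that the protocol waives premedication in course 2 or contradicts itself outright. It does neither. What stands is that the only sentence that makes premedication obligatory is narrower than the scheme around it.

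A second reply reads administration as course, which would make everything consistent. Section 6.1 does use the word that way when it equates the treatment day with visit 1 of a course. But Sections 4.1 and 5.2.3.2, and Section 6.1 itself where it speaks of doses, count infusions or doses within course 1, so this reading is weak.

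Third, 25 mg at course 4 could also come from 50 mg in course 2 followed by a single halving. That needs a reduction in course 2 that no text allows. The reply does show that the arithmetic supports the presumption without proving it.

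Fourth, a strict rule for two infusions may be deliberate: the starting rate, cardiac monitoring and surveillance rules in Sections 4.1, 5.2.5.1 and 6.1 also treat the first two infusions or doses as a unit. This is possible, but it does not explain why reduction and omission are permitted only from courses 3 and 5.

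The dose and rate comparisons should not be pressed either. On the default schedule the step into course 2 is only 1.01 to 1.11 times; the ratios above 2 belong to the contingent schedule; and the faster ramp depends on the investigator's judgement. Other protection remains: stopping and restarting at half the rate, glucocorticoids to treat reactions, 24-hour vital signs in the first two courses, DSMB assessment of the portions, and no taper after a reaction.

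**Conclusion.** The point holds. Section 4.1.4 presumes full premedication throughout courses 1 and 2, including a day 8 portion or split course 2 portions, but requires it only before the first two infusions. On the default schedule one infusion in those courses is left without a stated duty; with a three-portion course 1 it is two, and if both courses are given in three portions it is four. It should be corrected at the next amendment.

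Two stronger conclusions are not supported. The first is that the gap affects the trial's results: Section 5.2.1.1 excludes infusion-related reactions from the DLT definition, and code C2 removes no patient, so no estimate, analysis set or MTD rule changes. The second is that a number of avoidable reactions follows: the documents give no reaction rate, with or without premedication, so harm cannot be quantified.

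The conclusion rests on counting administrations as infusions, and for day 8 on the readable text, since some flow-chart rows are not legible in the public version. It does not depend on how the wording arose.

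**What to change.** Replace the scope of the duty in Protocol Section 4.1.4: premedication is obligatory 30-120 minutes before each infusion given in courses 1 and 2, naming the day 8 portion and every portion of a split course 2, unless contraindicated. Keep the taper from course 3 and the discretion in courses 5-8 as they are. The rate, cardiac monitoring and surveillance rules need no change. Apply the same rule in the medical review for SAP code C2. If the sponsor wants premedication on day 8 to be discretionary, the protocol should say so, and the C2 review should follow that instead.

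The cost is one sentence in an amendment and a note for the C2 review. The downside is slightly more steroid, antihistamine and antipyretic exposure in patients who would otherwise have gone without at these infusions. No new data are needed, because SAP Section 7.3 already lists premedication together with the drug administrations.
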